8.3. Lost to Follow-Up

A patient will be considered lost to follow-up if he or she repeatedly fails to return for scheduled visits and is unable to be contacted by the study site. Site personnel are expected to make diligent attempts to contact patients who fail to return for a scheduled visit or were otherwise unable to be followed up by the site.

9. Study Assessments and Procedures

Section 2 lists the Schedule of Activities, with the study procedures and their timing (including tolerance limits for timing).

9.1. Efficacy Assessments

9.1.1. Primary Effectiveness Assessments

The primary efficacy measure is the change in HbA1c from baseline to 24 weeks.

9.1.2. Secondary Effectiveness Assessments

The following secondary effectiveness measures will be collected at the time shown in the Schedule of Activities (Section 2):

- the change in HbA1c from baseline to 48 weeks
- proportion of patients who achieve HbA1c <7% at 24 and 48 weeks
- venous fasting plasma glucose (FPG) change from baseline at 24 and 48 weeks
- finger stick blood glucose (FSBG)-based fasting blood glucose (FBG), PPG change from baseline at 24 and 48 weeks
- daily insulin dose at 24 and 48 weeks
- body weight change from baseline at 24 and 48 weeks
- the severe, nocturnal and total hypoglycemia incidences and rates during the 24-week and 48-week treatment period
- time to insulin treatment change
- proportion of patients who achieve the HbA1c <7% without switching and discontinuing study insulin, and without using rescue therapy
- the change in Self-efficacy about Insulin Therapy Questionnaire (SEITQ) score from baseline at 48 weeks

9.1.3. Exploratory Effectiveness Assessments

- time to insulin discontinuation, switch, intensification or reduction in frequency
- proportion of patients who experience insulin discontinuation, switch, intensification or reduction in frequency during 48 weeks
- healthcare resource utilization (all-cause and T2DM-related; inpatient, outpatient and emergency room [ER]) during 48 weeks
- domain and total Insulin Treatment Satisfaction Questionnaire (ITSQ) score at 24 and 48 weeks
- the change in SEITQ score from baseline at 24 weeks

- the incidences and rates of other categories of hypoglycemia (documented symptomatic, asymptomatic, unspecified, probable symptomatic and relative hypoglycemia), if available, during the 24-week and 48-week treatment period

9.1.4. Appropriateness of Assessments

All effectiveness and safety measures assessed in this study are all well-established measures for insulin treatment.

Patient-reported outcomes measures (SEITQ, ITSQ) included in this study have been designed to provide information from the patient and the HCP perspective. Healthcare resource utilization assessments included in this study are acceptable methods for determining the impact of treatment/intervention from the payer perspective.

If a patient is unable to complete the questionnaire without assistance, someone not affiliated with the study may assist the patient in completing the questionnaire.

9.2. Adverse Events

Investigators are responsible for monitoring the safety of patients who have entered this study and for alerting Lilly or its designee to any event that seems unusual, even if this event may be considered an unanticipated benefit to the patient.

The investigator is responsible for the appropriate medical care of patients during the study.

Investigators must document their review of each laboratory safety report.

The investigator remains responsible for following, through an appropriate health care option, adverse events (AEs) that are serious or otherwise medically important, considered related to the investigational products or the study, or that caused the patient to discontinue the investigational products before completing the study. The patient should be followed until the event resolves, stabilizes with appropriate diagnostic evaluation, or is reasonably explained. The frequency of follow-up evaluations of the AE is left to the discretion of the investigator.

After the informed consent form (ICF) is signed, study site personnel will record via case report form (CRF) the occurrence and nature of each patient's preexisting conditions, including clinically significant signs and symptoms of the disease under treatment in the study. In addition, site personnel will record any change in the condition(s) and any new conditions as AEs. Investigators should record their assessment of the potential relatedness of each AE to protocol procedure and/or investigational product, via CRF.

The investigator will interpret and document whether or not an AE has a reasonable possibility of being related to study treatment, study device, or a study procedure, taking into account the disease and concomitant treatment or pathologies.

A "reasonable possibility" means that there is a cause and effect relationship between investigational products and/or study procedure and the AE.

The investigator answers yes/no when making this assessment.

Planned surgeries and nonsurgical interventions should not be reported as AEs unless the underlying medical condition has worsened during the course of the study.

If a patient's investigational product is discontinued as a result of an AE, study site personnel must report this to Lilly or its designee via CRF, clarifying if possible, the circumstances leading to any dosage modifications, or discontinuations of treatment.

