3.3. Benefit/Risk Assessment

More detailed information about the known and expected benefits and risks of study insulin treatments may be found in the package inserts of these insulin products.

4. Objectives and Endpoints

Table IOQR.2 shows the objectives and endpoints of the study.

Table IOQR.2. Objectives and Endpoints

Objectives	Endpoints
Primary	
1. To compare change in HbA1c from baseline to 24 weeks between insulin analog mid mixture BID and basal insulin analog QD treatments	1. The change in HbA1c from baseline to 24 weeks
Secondary	
2. To compare change in HbA1c from baseline to 48 weeks between insulin analog mid mixture BID and basal insulin analog QD treatments	2. The change in HbA1c from baseline to 48 weeks
3. To compare the proportion of patients who achieve HbA1c <7% at 24 and 48 weeks between insulin analog mid mixture BID and basal insulin analog QD treatments	3. Proportion of patients who achieve HbA1c <7% at 24 and 48 weeks
4. To compare the change in venous FPG from baseline to 24 and 48 weeks between insulin analog mid mixture BID and basal insulin analog QD treatments	4. Venous FPG change from baseline at 24 and 48 weeks
5. To compare the change in FSBG-based FBG and PPG from baseline to 24 and 48 weeks between insulin analog mid mixture BID and basal insulin analog QD treatments	5. FSBG-based FBG, PPG change from baseline at 24 and 48 weeks
6. To compare the daily insulin dose at 24 and 48 weeks between insulin analog mid mixture BID and basal insulin analog QD treatments	6. Daily insulin dose at 24 and 48 weeks
7. To compare the change in body weight from baseline to 24 and 48 weeks between insulin analog mid mixture BID and basal insulin analog QD treatments	7. Body weight change from baseline at 24 and 48 weeks
8. To compare the severe, nocturnal and total hypoglycemia incidences and rates during the 24-week and 48-week treatment period between insulin analog mid mixture BID and basal insulin analog QD treatments	8. The severe, nocturnal and total hypoglycemia incidences and rates during the 24-week and 48-week treatment period

Objectives and Endpoints

Objectives	Endpoints

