9.2.1.1. Suspected Unexpected Serious Adverse Reactions

Suspected unexpected serious adverse reactions (SUSARs) are serious events that are not listed in the investigator's brochure (IB) and that the investigator identifies as related to investigational products or procedure. Lilly has procedures that will be followed for the recording and expedited reporting of SUSARs that are consistent with global regulations and the associated detailed guidances.

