Appendix 3.1.2. Ethical Review

The investigator or an appropriate local representative must give assurance that the ethical review board (ERB) was properly constituted and convened as required by International Conference on Harmonisation (ICH) guidelines and other applicable laws and regulations.

Documentation of ERB approval of the protocol and the ICF must be provided to Lilly before the study may begin at the investigative site(s). Lilly or its representatives must approve the ICF, including any changes made by the ERBs, before it is used at the investigative site(s). All ICFs must be compliant with the ICH guideline on Good Clinical Practice (GCP).

The study site's ERB(s) should be provided with the following:

- the current package inserts and updates during the course of the study
- informed consent form
- relevant curricula vitae

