8.4.1. Adverse Event

General AEs will be collected in this study. Count and frequency of AEs will be summarized for overall study population and by treatment arm. Also, AEs as a cause for insulin treatment change will be collected, and summarized by treatment arm. Serious adverse events will be collected and reported per Lilly standard operating procedure (SOP) and local regulatory requirement. Count and frequency of SAEs will be summarized by treatment arm.

Adverse events (AEs) and treatment-emergent adverse events (TEAEs) will be coded using the MedDRA dictionary. AEs and TEAEs will be categorized by system organ class and preferred term and will be presented. TEAEs are defined as AEs occurring during or after the initial dose of study drug. AEs documented prior to initial dose cannot be classified as TEAEs unless there is a worsening in severity during or after the initial dose of study drug. The overall incidence of TEAEs with all causalities will be summarized as the number and percentage subjects in each of the categories: TEAE, TEAEs leading to insulin treatment change, SAE.

The following summaries will be presented at both the subject (number [%] of subjects) and event (number of events) level:

- AEs by SOC, PT, and treatment
- Treatment-emergent AEs by SOC, PT, and treatment
- Treatment-emergent AEs by SOC, PT, maximum severity, and treatment
- SAE by SOC, PT, and treatment
- SAE related to study drug by SOC, PT, and treatment

- Treatment-emergent AEs leading to treatment insulin treatment change by SOC, PT, and treatment
- Treatment-emergent AEs related to study drug by SOC, PT, and treatment

For the incidence at the subject level by SOC and PT, if a subject experiences more than one event within the same SOC and PT, only one occurrence will be included in the incidence.

For the incidence at the subject level by SOC, PT, and severity, if a subject experiences more than one event within the same SOC and PT, only the most severe occurrence will be included in the incidence.

For the incidence at the subject level by SOC, PT, and relationship to investigational product, if a subject experiences more than one event within the same SOC and PT, only the most related occurrence will be included in the incidence.

For the summary of number of events, if a subject experiences more than one event within the same SOC and PT, all events will be counted.

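### Protocol 9.2 defines a reasonable possibility of relatedness as actual causation, which may under-select related events, and 9.2.1.1 judges unexpectedness by a brochure identified for no study insulin

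*Protocol*

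**What the plan says.** **Relatedness.** Protocol 9.2 uses three wordings for one judgement.

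- For the CRF: "Investigators should record their assessment of the potential relatedness of each AE to protocol procedure and/or investigational product, via CRF".
- For the question itself, the investigator decides "whether or not an AE has a reasonable possibility of being related to study treatment, study device, or a study procedure".
- For the definition of the key term, a reasonable possibility "means that there is a cause and effect relationship between investigational products and/or study procedure and the AE".

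The response is binary: "The investigator answers yes/no when making this assessment". Protocol 9.2.1 words the test for SAEs before first dose and after discharge in terms of reasonable possibility, as the question does.

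**Use of the answer.** SAP 8.4.1 plans a table of "SAE related to study drug by SOC, PT, and treatment" and a matching one for treatment-emergent events. Protocol 9.2.1.1 makes the investigator's attribution part of the SUSAR definition.

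**Expectedness.** SUSARs are "serious events that are not listed in the investigator's brochure (IB) and that the investigator identifies as related to investigational products or procedure". Elsewhere, Protocol 3.3 says that risk information "may be found in the package inserts of these insulin products". Protocol 9.3 refers to the product label for overdose. Appendix 3.1.2 lists, among the documents for the ethics board, "the current package inserts and updates during the course of the study", and no brochure.

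**The concern.** A question about possibility and a definition that requires causation cannot both govern the same yes/no field. There is no middle category, so an investigator who follows the definition records a suspected but unproven reaction as unrelated. One who follows the question records it as related. The first practice empties the related-event tables of the cases they are meant to show. A mixture of the two makes the tables depend on who filled in the form, and treatment is open label (Protocol 7.3), so the threshold could also differ by arm.

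The second problem is separate. A serious related event counts as unexpected or not according to a reference document. If the reader cannot tell which document that is for the insulin the patient took, the classification is not reproducible.

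**Working it through.** No figure in the plan belongs to this point, so there is nothing to reproduce. The check compares the passages.

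**Step 1: is the definition an outlier?** The CRF instruction in 9.2 speaks of potential relatedness. The question in 9.2 speaks of a reasonable possibility. The pre-dose and post-discharge rules in 9.2.1 use the same standard as the question. Only the defining sentence asserts that a causal link exists, with no *may* or *could*. It is the outlier, but it is also the sentence that purports to give the term its meaning.

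**Step 2: what depends on the answer?**

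| Use | Place | Depends on relatedness? |
|---|---|---|
| Related TEAE and related SAE tables | SAP 8.4.1 | Yes |
| SUSAR classification | Protocol 9.2.1.1 | Yes |
| SAE after consent but before first dose | Protocol 9.2.1 | Yes (study procedure) |
| SAE learned of after discharge | Protocol 9.2.1 | Yes |
| SAE after first dose, to the sponsor within 24 hours | Protocol 9.2.1 | No |
| All-causality AE, TEAE and SAE tables | SAP 8.4.1 | No |
| Hypoglycemia incidence and rates | Protocol 10.3.4, SAP 8.4.4 | No |
| Primary and secondary efficacy analyses | SAP 8.2 | No |

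**Step 3: direction and size.** Let R be the number of patients with at least one suspected event, and f the share of them for whom the investigator regards causation as established. Under the question, a related-event table shows R patients. Under the literal definition it shows f × R. Since f lies between 0 and 1, the count can stay the same or fall; it cannot rise. The documents give neither R nor f, so the shortfall lies anywhere from 0 (f = 1) to R (f = 0).

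**Step 4: which document decides expectedness?** The investigator's brochure appears in 9.2.1.1 and otherwise only in the abbreviation list (Appendix 1). Protocol 7.1 treats all insulins used in the study as investigational products and gives four examples in two classes. Protocol 7.1.1 says that they are on the market and not supplied by the study. No brochure is tied to any of them, and the safety information named elsewhere is the insert or the label. How often the two sources would classify an event differently, and in which direction, cannot be worked out without seeing them.

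**The case against.** The strongest reply is that one clumsy sentence sits among several that state the usual suspicion standard, and that experienced investigators will apply that standard. This is plausible, and it is why the finding is a risk and not a demonstrated error in the data. It does not remove the contradiction: a site that follows the definition is following the protocol.

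The second reply is that safeguards exist. Every SAE after first dose reaches the sponsor within 24 hours whatever its cause. Sites must also report anything unusual. The sponsor's expedited-reporting procedures are said to follow global regulations. All-causality tables are planned. These points stand and limit the consequence. They do not repair the two related-event tables or change the wording of the SUSAR definition, and the pre-dose and post-discharge rules have no causality-free counterpart.

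On the brochure, it is fair to say that Protocol 3.3, 9.3 and Appendix 3.1.2 serve other purposes (benefit and risk, overdose, ethics submission), and none of them sets an expectedness reference. Protocol 9.2.1 also sends adverse reactions to other manufacturers' drugs to regulators or authorization holders as in normal practice. That route depends neither on the brochure nor on the definition. However, 7.1 makes those insulins investigational products as well, so the SUSAR rule covers them too and its reference document still has to be named.

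A reader might infer that the plan selects the wrong events, that possible serious reactions will not be expedited, or that no brochure exists. The documents support none of these. The literal definition would leave events out, not choose a different set. The sponsor's procedures are not visible. A brochure may exist that the protocol does not identify.

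**Conclusion.** The concern holds in a limited form. The definition in Protocol 9.2 contradicts the question it defines and the related wording in 9.2 and 9.2.1. If applied as written, it may under-select events for the two related-event tables, for SUSAR classification, and for SAE reporting before first dose and after discharge. The conclusion about direction assumes that some investigators apply the sentence literally. Its size cannot be determined from the documents.

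The expectedness reference in 9.2.1.1 is not reconciled with the safety documents named elsewhere. Neither the size nor the direction of any effect can be stated. It would be tempting to say that labelled reactions will be expedited as unexpected, or unlabelled ones missed, but that needs a comparison of brochure and inserts that the documents do not allow.

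The primary conclusion, the other efficacy analyses and the hypoglycemia comparison are untouched. The correction is worth making because the rule as stated is wrong and the change is small.

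**What to change.** - **Protocol 9.2:** redefine the term so that a reasonable possibility means a cause and effect relationship is plausible on the available facts (such as timing, underlying disease and other treatment) and need not be established. Carry the same sentence into the CRF completion guide.
- **Protocol 9.2.1.1:** reconcile the expectedness reference with 3.3 and Appendix 3.1.2. Name the current package insert of the insulin the patient was receiving at onset or, if a brochure does apply, say which one and to which product.
- **Procedure-related events:** handle these separately in 9.2.1.1, because an insulin insert does not cover them.

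The SAP tables need no change. The cost is a few sentences in an amendment and in the CRF guide. Somewhat more events will be classed as related, and the inserts of all insulins in use must be kept on file.

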9.2.1. Serious Adverse Events

An SAE is any AE from this study that results in one of the following outcomes:

- death
- initial or prolonged inpatient hospitalization
- a life-threatening experience (that is, immediate risk of dying)
- persistent or significant disability/incapacity
- congenital anomaly/birth defect
- considered significant by the investigator for any other reason: important medical events that may not result in death, be life-threatening, or require hospitalization may be considered serious, based upon appropriate medical judgment.

Although all AEs occurring after signing the ICF are recorded in the CRF, serious adverse event (SAE) reporting begins after the patient has signed the ICF and has received investigational product. However, if an SAE occurs after signing the ICF, but prior to receiving investigational product, it needs to be reported ONLY if it is considered reasonably possibly related to study procedure.

Study site personnel must alert Lilly or its designee of any SAE within 24 hours of investigator awareness of the event via a sponsor-approved method. If alerts are issued via telephone, they are to be immediately followed with official notification on study-specific SAE forms. This 24-hour notification requirement refers to the initial SAE information and all follow-up SAE information.

Pregnancy (during maternal or paternal exposure to investigational products) does not meet the definition of an AE. However, to fulfill regulatory requirements any pregnancy should be reported following the SAE process to collect data on the outcome for both mother and fetus.

Investigators are not obligated to actively seek AEs or SAEs in subjects once they have discontinued and/or completed the study (the patient summary CRF has been completed). However, if the investigator learns of any SAE, including a death, at any time after a subject has been discharged from the study, and he/she considers the event reasonably possibly related to the study treatment or study participation, the investigator must promptly notify Lilly.

Investigators or other study personnel are requested to report adverse reactions in temporal association with Lilly drugs not under evaluation and with any non-Lilly drugs to the appropriate

party (for example, regulators or local market authorization holder) as they would in normal practice as required by applicable laws, regulations, and practices.

9.2.1.1. Suspected Unexpected Serious Adverse Reactions

Suspected unexpected serious adverse reactions (SUSARs) are serious events that are not listed in the investigator's brochure (IB) and that the investigator identifies as related to investigational products or procedure. Lilly has procedures that will be followed for the recording and expedited reporting of SUSARs that are consistent with global regulations and the associated detailed guidances.

9.2.2. Complaint Handling

Lilly collects product complaints on investigational products and drug delivery systems used in clinical studies in order to ensure the safety of study participants, monitor quality, and to facilitate process and product improvements.

Patients will be instructed to contact the investigator as soon as possible if he or she has a complaint or problem with the investigational products or drug delivery system so that the situation can be assessed.

Investigators are instructed to report product complaints related to marketed products directly to the manufacturer following package inserts.

9.3. Treatment of Overdose

Refer to the product label of study insulins for advice on overdose.

9.4. Safety

9.4.1. Hypoglycemia

Patients will be trained about signs and symptoms of hypoglycemia, how to treat hypoglycemia, and how to collect appropriate information in the study diary according to the Schedule of Activities (Section 2). Hypoglycemia will be classified as follows (ADA 2005) (Note: the blood glucose (BG) concentrations listed below refer to values reported by a laboratory or obtained with FSBG meter):

- **Documented symptomatic hypoglycemia:** An event during which typical symptoms of hypoglycemia are accompanied by BG ≤ 70 mg/dL (≤ 3.9 mmol/L).
- **Asymptomatic hypoglycemia:** An event not accompanied by typical symptoms of hypoglycemia but with BG ≤ 70 mg/dL (≤ 3.9 mmol/L).
- **Unspecified hypoglycemia:** An event during which BG ≤ 70 mg/dL (≤ 3.9 mmol/L) but no information relative to symptoms of hypoglycemia was recorded
- **Severe hypoglycemia:** An event requiring assistance of another person to actively administer carbohydrate, glucagon, or other resuscitative actions. During these episodes the patient has an altered mental status and cannot assist in their care, is semiconscious or

unconscious or experienced coma with or without seizures, and may require parenteral therapy. Plasma glucose measurements may not be available during such an event, but neurological recovery attributable to the restoration of BG concentration to normal is considered sufficient evidence that the event was induced by a low BG concentration (BG \leq 70 mg/dL [\leq 3.9 mmol/L]).

- **Nocturnal hypoglycemia:** Any hypoglycemic event (documented hypoglycemia or probable symptomatic hypoglycemia, including severe hypoglycemia) that occurs between bedtime and waking. This is consistent with the ADA recommendations of reporting events that occur during sleep (ADA 2005). It is also important to collect the actual time when a hypoglycemic event occurred to allow further characterization of hypoglycemia timing (for example, to qualify the hypoglycemic events that are occurring between midnight to 6 AM or to look at frequency of events occurring across a 24-hour clock).
- **Probable symptomatic hypoglycemia:** An event during which symptoms indicative of hypoglycemia are not accompanied by a BG determination (but that was presumably caused by BG \leq 70 mg/dL [\leq 3.9 mmol/L]).
- **Relative hypoglycemia:** An event during which typical symptoms of hypoglycemia, that do not require the assistance of another person, are accompanied by BG $>$ 70 mg/dL ($>$ 3.9 mmol/L), but these levels may be quickly approaching the 70 mg/dL (3.9 mmol/L) threshold. The BG level of patients with chronically poor glycemic control can decrease so rapidly that patients may report symptoms of hypoglycemia before their BG concentration is $<$ 70 mg/dL ($<$ 3.9 mmol/L). The evaluation of this category is optional. However, if a patient reports a relative hypoglycemia event where assistance from another person was received or the patient experienced significant symptoms, the study team should clarify the circumstances to ensure the event is not a severe hypoglycemia event, and report it appropriately.
- **Total hypoglycemia:** This optional category combines all cases of hypoglycemia (documented hypoglycemia or probable symptomatic hypoglycemia, including severe hypoglycemia) excluding the events of relative hypoglycemia. Nocturnal and severe hypoglycemia are special cases of documented or probable hypoglycemia. If an event of hypoglycemia falls into multiple subcategories, that event should only be counted once in this category.

All episodes of hypoglycemia should be recorded in the “Hypoglycemic Episodes” section of the electronic case report form (eCRF). If a hypoglycemic event meets the criteria of SAE (Section 9.2.1), it should also be recorded on “Serious Adverse Events” section of the eCRF (that is, recorded as an SAE).

Severe, nocturnal and total hypoglycemia events will be collected and analyzed as secondary endpoints. Other categories of hypoglycemia (documented symptomatic, asymptomatic, unspecified, probable symptomatic and relative hypoglycemia) events will be collected if available and analyzed as exploratory objectives.

